---

**Statement of Compliance**

This clinical trial will be conducted in compliance with all stipulation of this protocol, the conditions of the ethics committee approval, the NHMRC National Statement on ethical Conduct in Human Research (2007 and all updates), the Integrated Addendum to ICH E6 (R1): Guideline for Good Clinical Practice E6 (R2), dated 9 November 2016 annotated with TGA comments and the NHMRC guidance Safety monitoring and reporting in clinical trials involving therapeutic goods (EH59, 2016).

This clinical trial is not sponsored by any pharmaceutical company or other commercial entity.

---

## PROTOCOL SYNOPSIS

TITLE	Can Vitamin C prevent Complex Regional Pain Syndrome in lower limb trauma? A double-blinded randomised, controlled feasibility study.
TRIAL DESCRIPTION	
This is a randomised controlled feasibility trial conducted at five sites:
 

• Peninsula Health

• Frankston Private Hospital

• Holmesglen Private Hospital

• Cabrini Brighton Private Hospital

• Beleura Private Hospital

 
The trial will recruit patients who present for elective and emergency surgery of the foot and ankle. Patients will be randomised into two groups – placebo and 500mg vitamin C. Patients will then be assessed at regular intervals up to six months post injury/surgery to determine whether chronic regional pain syndrome was diagnosed.

OBJECTIVES	
Primary objective – to determine if the proposed protocol is feasible with regards to:
 

• Recruitment capability

• Data collection procedure

• Suitability of intervention

• Resource availability

• Participant response

 
Secondary objectives:
 

1. to determine if vitamin C prevents CRPS in patients with lower limb extremity trauma in a dose-response manner

2. to determine the incidence of CRPS in lower limb extremity trauma and elective surgery.

3. To determine the demographics and characteristics of patients who develop CRPS of the lower limb

OUTCOMES AND OUTCOME MEASURES	
The outcome is development of CRPS at any stage following trauma or surgery within the six-month time frame. The outcome measure is the validated Clinical Diagnostic Criteria for CRPS, also known as the ‘Budapest Criteria’(1).

TRIAL POPULATION	
Adult patients (defined as aged 18 and over) who undergo elective or trauma surgery on their foot and ankle at the following sites:
 

• Peninsula Health

• Frankston Private Hospital

	
 
• Holmesglen Private Hospital
 
• Cabrini Brighton Private Hospital
 
• Beleura Private Hospital
 
 
Patients who are unable to provide informed consent will not be enrolled in the study.

DESCRIPTION OF SITES ENROLLING PARTICIPANTS	
 
• Peninsula Health (Frankston public hospital)
 
• Frankston Private Hospital
 
• Holmesglen Private Hospital
 
• Cabrini Brighton Private Hospital
 
• Beleura Private Hospital
 

DESCRIPTION OF INTERVENTIONS	
Patients will be allocated to one of two groups:
 
 
• Placebo
 
• Vitamin C 500mg daily
 
 
50 capsules will be given to a patient in a box and patients will be asked to take one capsule daily for fifty days.

TRIAL DURATION	
It is expected the trial will take 12 months to complete.
 
Patients will be enrolled for six months and it is expected the trial will take six months to recruit appropriate numbers.
 
Data analysis is expected to take six months.

PARTICIPANT DURATION	
Participants are enrolled in the study for six months from the date of their index surgery. Patients will be reviewed at four points post-operatively:
 
 
• between 7 and 14 days, combined with post-operative wound check and provision of standard post-operative orthotics/devices
 
• five to six weeks, combined with post-operative x-ray if appropriate
 
• eleven to fourteen weeks
 
• twenty-six weeks following their injury
 

---

## GLOSSARY OF ABBREVIATIONS

ABBREVIATION	TERM
AR	Adverse Reaction
CRF / eCRF	Case Report Form / electronic Case Report Form
CRPS	Complex regional pain syndrome
DMC SMC	Data Monitoring Committee / Safety Monitoring Committee
DSMB	Data Safety Monitoring Board
FDA	Food and Drug Administration
GCP	Good Clinical Practice
GLP	Good Laboratory Practices
GMP	Good Manufacturing Practices
HREC	Human Research Ethics Committee
ISO	International Organization for Standardization
ITT	Intention To Treat
MedDRA	Medical Dictionary for Regulatory Activities
MSDS	Material Safety Data Sheet
NHMRC	National Health and Medical Research Council
NSAIDS	Non-steroidal Anti-Inflammatory Drugs
PI / CPI	Principal Investigator / Coordinating or Chief Principal Investigator
PI	Product Information (available for an approved drug or device)
QA	Quality Assurance
QC	Quality Control
RGO	Research Governance Office
SAE	Serious Adverse Event
SAP	Statistical Analysis Plan
SAR	Serious Adverse Reaction
SMC	Safety Monitoring Committee
SoA	Schedule of Assessments
SOP	Standard Operating Procedure
SSI	Significant Safety Issue
SUSAR	Suspected Unexpected Serious Adverse Reaction
TGA	Therapeutic Goods Administration
UAR	Unexpected Adverse Reaction
USM	Urgent Safety Measure

## 1. ADMINISTRATIVE INFORMATION

### 1.1. Trial registration

#### 1.1.1. Trial registry

The trial will be registered with the Australian New Zealand Clinical Trials Registry (ANZCTR).

### 1.3. Expected duration of study

The recruitment period will be six months. The length of the treatment period is fifty days and the follow-up period is six months. It is expected the study will be completed within twelve months.

### 1.5. Stakeholder involvement

Investigators have engaged with the following stakeholders:

- Orthopaedic Department at Peninsula Health
- Podiatry Department at Peninsula Health
- Allied health employees of South East Orthopaedic Surgery
- Chief Executive Officer of the following private hospitals:
  - Frankston Private Hospital
  - Beleura Private Hospital
  - Holmesglen Private Hospital
  - Cabrini Private Hospital

The investigators have discussed the nature of the trial with these key stakeholders and incorporated preliminary feedback. The investigators will continue to engage with these stakeholders for ongoing feedback given the nature of the feasibility trial.

---

## 2. INTRODUCTION AND BACKGROUND

### 2.1. Trial rationale and aim

We aim to perform a feasibility study, with the potential for a larger trial in the future.

Primary objective – to determine if the proposed protocol is feasible with regards to:

- Recruitment capability
- Data collection procedure
- Suitability of intervention
- Resource availability
- Participant response

Secondary objective:

- to determine if vitamin C prevents CRPS in patients with lower limb extremity trauma in a dose-response manner
- to determine the incidence risk of CRPS in lower limb extremity trauma and elective surgery

The role of vitamin C and the prevention of CRPS has been demonstrated in upper limb trauma(2) but not clearly proven in lower limb trauma and elective surgery. A randomised controlled trial is yet to be published on this important topic, but several quasi-randomised trials have demonstrated the efficacy and safety of vitamin C in CRPS prevention(3)(4).

It is the experience of the senior author that complex regional pain syndrome was a common complication of lower extremity trauma and any means to prevent this debilitating disease was worth investigating to see if a simple, cheap intervention such as vitamin C, which has been demonstrated to prevent CRPS in upper limb trauma, would also be effective in lower limb trauma.

As a trial of this nature has not been conducted before, a feasibility trial is appropriate to assess the effectiveness of the protocol.

### 2.2. Background

Complex regional pain syndrome can be debilitating for patients. It is described as sustained sympathetic activity in a perpetuated reflex arc characterised by pain out of proportion to examination findings(5). It is commonly associated with crush injuries, surgery and prolonged immobilisation. The condition responds poorly to conservative and surgical treatments and is frustrating for both patient and clinician to treat. Early diagnosis and treatment is generally associated with better outcomes, but diagnosis is often delayed(6). Preventative treatment is the mainstay of therapy due to the poor clinical response of the condition following diagnosis and prolonged recovery rate with severe cases(7).

Type I CRPS is more common and is not associated with any demonstrable nerve lesions. It can be associated with trauma, casting or compression bandaging. Type II CRPS occurs in the setting of identifiable nerve injury(8).

The pathophysiology of the condition is still poorly understood. In patients who have sustained major trauma, standard homeostasis can be inundated resulting in a massive

---

systemic inflammatory response. Complex regional pain syndrome and burn wounds can involve a similar cascade of inflammatory exaggeration and severe symptoms including severe swelling, skin changes, hyperaemia and pain. Patients experience a triad of sensory, motor and autonomic nervous dysfunctions with long-standing pain and temperature differences of the affected and contralateral limb(9). An increase in inflammatory markers such as TNF-alpha and calcitonin are present both locally and systemically.

CRPS can affect patients of all ages with a 4:1 female to male ratio and median age of 46 years at onset(10). The incidence has been described as up to 37% following distal radius fractures and 30% following tibial shaft fractures. Trauma is the commonest precipitating event(8).

Current treatment is generally via a multidisciplinary team. At Peninsula Health, this involves a physiotherapist, pain specialist and hand therapist or podiatrist depending on the extremity. The goals of treatment are pain control, rehabilitation, restoration of function and preservation of current function. Anti-epileptic medication such as gabapentin is commonly prescribed and has been shown to have reduction of symptoms(11). Antidepressants and non-steroidal anti-inflammatory medication have also been described with limited effectiveness. Topical agents such as lidocaine patches have not been studied in a controlled trial but are part of the treatment process. Nerve blocks, peripheral nerve stimulation and spinal cord stimulation have also been described. Physiotherapy and occupational therapy are the mainstay of treatment and aim to control oedema, stretch the affected limb to prevent contraction. Massage, contrast baths and transcutaneous electrical stimulation can be used to desensitize the affected limb. There is good-quality evidence to support physiotherapy management in CRPS patients(9).

It was noted that vitamin C given in high doses during the first twenty-four hours of burn resuscitation reduced resuscitation fluid requirements and wound oedema. Vitamin C has been shown to scavenge hydroxyl free radicals which protects the delicate vascular epithelium and inhibits vascular permeability and subsequently reduces oedema(12). Zollinger et al extrapolated this theory to upper limb trauma and demonstrated a dose-response reduction in complex regional pain syndrome in distal radius fractures in a large multi-centre randomised controlled trial(2). Besse et al (2009) performed a quasi-randomised prospective trial that also demonstrated a dose-response relationship between vitamin C and the prevention of CRPS(3).

Zollinger described a statistically significant reduction in the diagnosis of CRPS in patients taking 500mg of vitamin C with no statistically significant difference between patients taking 500mg and 1000mg, but a difference between placebo and 250mg(3). In Australia, the most common available dose of vitamin C in capsule is 500mg. The efficacy and safety of Vitamin C in this dosage has been demonstrated(4). For this feasibility study we are therefore randomising patients to placebo and vitamin C 500mg.

Valid outcome measures of CRPS have been described(13)(14). Similar to the protocol described by Zollinger(2), patients will undergo a clinical assessment two weeks post injury, six weeks post injury, twelve weeks post injury and twenty-six weeks post-injury. This

---

correlates to standard routine practice, where patients are assessed at two weeks post-operatively for a wound check, six weeks post-operatively for clinical review and also commonly twelve and twenty-six weeks post-operatively for ongoing assessment of response to surgery.

Patients will be assessed by their treating clinician according to the Budapest Criteria(1):

- A: continuing pain, which is disproportional to any inciting event
- B: The patient must report at least one symptom in three of the four following categories:
  - Sensory- reports of hyperaesthesia and/or allodynia
  - Vasomotor – reports of temperature asymmetry and/or skin colour changes and/or skin colour asymmetry
  - Sudomotor/oedema – reports of oedema and/or sweating changes and/or sweating asymmetry
  - Motor/trophic – reports of decreased range of motion and/or motor dysfunction (weakness/tremor/dystonia) and/or trophic changes (hair/nail/skin)
- C: The clinician must observe at least one sig at the time of the evaluation in two or more of the following categories:
  - Sensory- evidence of hyperalgesia (to pinprick) and/or allodynia and/or deep somatic pressure and/or joint movement
  - Vasomotor – evidence of temperature asymmetry and/or skin colour changes and/or skin colour asymmetry
  - Sudomotor/oedema – evidence of oedema and/or sweating changes and/or sweating asymmetry
  - Motor/trophic – evidence of decreased range of motion and/or motor dysfunction (weakness/tremor/dystonia) and/or trophic changes (hair/nail/skin)
- D: There is no other diagnosis that better explains the signs and symptoms

A randomised controlled trial to investigate the dose-response relationship between vitamin C and the prevention of complex regional pain syndrome in the lower limb has yet to be reported in the literature and can potentially revolutionise how we treat these patients. It is a relatively cheap, safe, potentially effective preventative in lower limb trauma that may help prevent the catastrophic consequences of complex regional pain syndrome in the lower limb.

## 2.3. Risk/Benefit assessment

### 2.3.1. Known potential risks

Trauma is known to increase vitamin C requirements. However, in patients exceeding 1000mg of vitamin C daily the multivariate relative risk of kidney stone formation in men was 41% higher than in those consuming 90mg a day. Vitamin C in high doses (in excess of 5000mg a day) has been suggested to cause haemolysis in glucose-6-phosphatase dehydrogenase deficient patients, which has a high prevalence rate amongst persons of

---

African, Asian or Mediterranean descents(15). Neither Zollinger nor Besse described any complications from their vitamin C dosing (maximum 1000mg) in their published trials (2)(3).

### **2.3.2. Known potential benefits**

Vitamin C has been proven to prevent the development of complex regional pain syndrome in patients who experience upper limb trauma. Should this finding be extrapolated to the lower limb, there will be a lower rate of this condition in the trial population. The side effects of opioid analgesia and non-steroidal anti-inflammatory medication (NSAID's) are well known and more severe than vitamin C(16). It is therefore reasonable that the potential analgesic benefits of vitamin C are considered.

### **2.3.3. Assessment of potential risks and benefits**

Vitamin C is a relatively safe, commonly taken, over-the-counter vitamin supplement given to children and adults. Vitamin C is available in Australia and New Zealand without a prescription in chemists in doses of up to 1000mg. It is also the experience of the senior author that patients are 'prescribed' vitamin C by some local naturopaths in massively high doses, in excess of 2000mg daily. Despite these high doses, complications were not noted by the senior author. There have been described cases of kidney stones in high doses (>1000mg a day)(9). In massively high doses (up to 10 times our proposed intervention dose) it can be associated with haemolysis in glucose-6-phosphatase dehydrogenase deficiency. Renal failure has been reported in massively high doses (up to 100 times what we are proposing) given intravenously(17).

Previous studies of vitamin C in the doses we are proposing have not described any complications in patients taking the supplement. The potential benefit (prevention of a debilitating, difficult-to-treat condition in both the study population and in future patients), far outweigh the risks of a vitamin supplement that many people take as an over-the-counter medication.

## **3 TRIAL OBJECTIVES AND OUTCOMES**

### **3.1 Objectives**

#### **3.1.1 Primary objective**

Primary objective – to determine if the proposed protocol is feasible with regards to:

- Recruitment capability
- Data collection procedure
- Suitability of intervention
- Resource availability
- Participant response

#### **3.1.2 Secondary objectives**

Secondary objective:

1. to determine if vitamin C prevents CRPS in patients with lower limb extremity trauma in a dose-response manner

2. to determine the incidence of CRPS in lower limb extremity trauma.
3. To determine the demographics and characteristics of patients who develop CRPS of the lower limb

### 3.1.3 Exploratory objectives

There are no exploratory objectives for this study.

## 3.2 Outcomes

**Table listing objectives and outcomes**

OBJECTIVE	OUTCOME & OUTCOME MEASURE
Primary	
Primary objective – to determine if the proposed protocol is feasible with regards to: 
 
• Recruitment capability
 
• Data collection procedure
 
• Suitability of intervention
 
• Resource availability
 
• Participant response
 
	Recruitment capability: 
 
• Successful recruitment of pre-determined patient numbers
 
 Data collection procedure: 
 
• Successful follow up at established time-points
 
• Qualitative clinical feedback about ease of assessment/data collection
 
• Lost to follow up rate
 
 Suitability of intervention: 
 
• Patient-reported compliance with medication
 
• Patient-reported complication
 
• Qualitative assessment of patient feedback
 
 Resource availability 
 
• Establishing paid and unpaid labour costs required for the trial
 
• Availability of medication and placebo
 
 Participant response: 
 
• Qualitative participant feedback
 
• Participant engagement/follow up
 

Secondary	

 
1. To determine if vitamin C prevents CRPS in patients with lower limb extremity trauma in a dose-response manner
 
2. to determine the incidence of CRPS in lower limb extremity trauma
 
	To determine if vitamin C prevents CRPS in patients with lower limb extremity trauma in a dose-response manner: Patients are evaluated at four points post-operatively: 
 
• 10-14 days
 
• 5-6 weeks
 
• 10-12 weeks
 
• 26 weeks
 
 The outcome of a positive diagnosis for CRPS will be made if the patient meets the 'Budapest criteria' at any of their four post-operative review appointments. This is a combination of asking patients about their symptoms and

OBJECTIVE	OUTCOME & OUTCOME MEASURE
	
examining them for positive signs as per the below criteria:
 
A: continuing pain, which is disproportional to any inciting event
 
B: The patient must report at least one symptom in three of the four following categories:
 
 
• Sensory- reports of hyperaesthesia and/or allodynia
 
• Vasomotor – reports of temperature asymmetry and/or skin colour changes and/or skin colour asymmetry
 
• Sudomotor/oedema – reports of oedema and/or sweating changes and/or sweating asymmetry
 
• Motor/trophic – reports of decreased range of motion and/or motor dysfunction (weakness/tremor/dystonia) and/or trophic changes (hair/nail/skin)
 
 
C: The clinician must observe at least one sig at the time of the evaluation in two or more of the following categories:
 
 
• Sensory- evidence of hyperalgesia (to pinprick) and/or allodynia and/or deep somatic pressure and/or joint movement
 
• Vasomotor – evidence of temperature asymmetry and/or skin colour changes and/or skin colour asymmetry
 
• Sudomotor/oedema – evidence of oedema and/or sweating changes and/or sweating asymmetry
 
• Motor/trophic – evidence of decreased range of motion and/or motor dysfunction (weakness/tremor/dystonia) and/or trophic changes (hair/nail/skin)
 
 
D: There is no other diagnosis that better explains the signs and symptoms
 
This outcome method has been validated(1).

To determine the demographics and characteristics of patients who develop CRPS of the lower limb
	
Patient demographics will be collected:
 
 
• Age
 
• Gender
 
• Mechanism of injury (high energy/low energy)
 
• Workers compensation injury
 
• Smoking status
 

OBJECTIVE	OUTCOME & OUTCOME MEASURE
	
 
• Diabetes
 
• Pre-existing history of CRPS
 
 
This information will be used to comment on the demographic of patients who do develop complex regional pain syndrome with the aim of predicting and preventing the condition in this patient population.

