  - Compensable status (public patient, private health insurance, self-funded patient in private, workers' compensation, TAC, other)
- Surgical demographics
  - Date of surgery
  - Hospital where surgery was performed
  - Surgery type (elective, emergency, other)
  - Surgical site (forefoot, midfoot, hindfoot, tibia, combination, other)

The trial intervention will be administered by a researcher and commenced within 72 hours of surgery or injury. In the event that a patient sustains an injury the subsequently has surgery, their 72 hour 'clock' will commence immediately following their surgery.

At each trial visit, patients will be assessed as per the outcome criteria. Patients will be asked about their symptoms and examination documented by the clinician to specifically address the Budapest Criteria for CRPS diagnosis:

A: Does the patient report a history of:	 sensory changes (hyperaesthesia and/or allodynia)  vasomotor changes (temperature asymmetry, skin colour changes and/or skin colour asymmetry)  sudomotor/oedema changes (oedema, sweating changes or sweating asymmetry)  motor/trophic changes (decreased range of motion and/or motor dysfunction and/or weakness/tremor/dystonia and/or trophic changes of hair/nails/skin?)
B: Does the clinician observe:	 sensory changes (hyperaesthesia and/or allodynia)  vasomotor changes (temperature asymmetry, skin colour changes and/or skin colour asymmetry)  sudomotor/oedema changes (oedema, sweating changes or sweating asymmetry)  motor/trophic changes (decreased range of motion and/or motor dysfunction and/or weakness/tremor/dystonia and/or trophic changes of hair/nails/skin?)
C: Is there another diagnosis that better explains the signs and symptoms during today's history and examination?	 Yes  No
D: Is the patient's pain disproportionate to the inciting event?	 Yes  No
If the patient responds yes to three out of four questions in part A, AND the clinician observes two out of four signs in part B, AND answers yes to C and D, the patient meets the criteria for CRPS diagnosis.	 Yes  No
Does the patient meet the criteria for CRPS diagnosis?	

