Patients will be examined at their review appointment by a member of the research team or treating clinician according to the following Budapest Criteria:

- A: continuing pain, which is disproportional to any inciting event
- B: The patient must report at least one symptom in three of the four following categories:
  - Sensory- reports of hyperaesthesia and/or allodynia
  - Vasomotor – reports of temperature asymmetry and/or skin colour changes and/or skin colour asymmetry
  - Sudomotor/oedema – reports of oedema and/or sweating changes and/or sweating asymmetry
  - Motor/trophic – reports of decreased range of motion and/or motor dysfunction (weakness/tremor/dystonia) and/or trophic changes (hair/nail/skin)
- C: The clinician must observe at least one sig at the time of the evaluation in two or more of the following categories:
  - Sensory- evidence of hyperalgesia (to pinprick) and/or allodynia and/or deep somatic pressure and/or joint movement
  - Vasomotor – evidence of temperature asymmetry and/or skin colour changes and/or skin colour asymmetry
  - Sudomotor/oedema – evidence of oedema and/or sweating changes and/or sweating asymmetry

- 
- Motor/trophic – evidence of decreased range of motion and/or motor dysfunction (weakness/tremor/dystonia) and/or trophic changes (hair/nail/skin)
  - D: There is no other diagnosis that better explains the signs and symptoms

If a patient is unable to attend their appointment in person, a Telehealth appointment and videoconference examination will be utilised instead of a face-to-face appointment.

This information will be recorded in RedCap database managed by Monash University. Patients who meet the above criteria will be diagnosed with complex regional pain syndrome and referred to physiotherapy for management of this condition. They will be told to continue their treatment medication. Patients will then be removed from the trial follow-up (as you cannot have CRPS twice from the same event).

Patients diagnosed with CRPS will be communicated to the lead researcher via email and subsequently entered into the trial database as meeting the outcome.

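### A CRPS positive at the first post-operative visit is final and never re-checked, and the form that scores it does not match the protocol's own criteria

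*Protocol*

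**What the plan says.** **Event rule.** The table in section 3.2 makes CRPS an event if the Budapest criteria are met "at any of their four post-operative review appointments". The protocol states no confirming visit, minimum time from surgery or adjudication.

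**First visit.** The synopsis places it "between 7 and 14 days, combined with post-operative wound check". The table in section 3.2 gives 10-14 days instead.

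**After a positive.** Section 7.4 has the patient referred to physiotherapy and kept on the capsules. It continues: "Patients will then be removed from the trial follow-up (as you cannot have CRPS twice from the same event".

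**Criteria in the text.** Sections 2.2, 3.2 and 7.4 list four criteria. The first is "A: continuing pain, which is disproportional to any inciting event" and the last is "D: There is no other diagnosis that better explains the signs and symptoms". Between them stand symptoms in three of four categories and signs in two of four.

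**Criteria on the form.** The form in sections 7.4 and 9.2.2 re-letters the items. Its pain item is "D: Is the patient's pain disproportionate to the inciting event". Its item C asks whether another diagnosis explains the findings better. The scoring sentence then requires a yes to both C and D.

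**Analysis.** Section 11.3 compares arms by Cox regression on time to diagnosis and reports six-month incidence as a proportion. Its one sensitivity analysis of the case definition uses individual Budapest criteria, which loosens the definition and does not test persistence.

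**The concern.** The first visit is where a CRPS call is hardest to make. Oedema, skin colour change and reduced movement each fill a category on the form. It is a clinical assumption, not protocol text, that they are common one to two weeks after foot and ankle surgery. If they are present, the symptom and sign counts can be met by recovery alone. The diagnosis then rests on two yes/no judgements, about disproportion and about a better explanation. As printed, the second of these is scored backwards.

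A wrong call at that visit cannot be corrected, because CRPS is not assessed again. It also falls within about the first two weeks of a fifty-day course. Under blinding such errors should occur about equally in both arms, so they add the same number of false events to each. Incidence rises and the comparison moves toward no effect. Both quantities are stated secondary objectives, and section 2.1 has a larger trial in view.

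**Working it through.** **1. Is there a planned figure to reproduce?** No. Section 11.1 sets at least 50 per arm by judgement, without alpha, power or effect size. 2 x 50 = 100 agrees with the approximately 100 in section 4.7.

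**2. Form against criteria.** Suppose the symptom and sign counts are met.

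| Better diagnosis? (item C) | Disproportionate pain? (item D) | Protocol criteria | Form as printed |
|---|---|---|---|
| No | No | not CRPS | not CRPS |
| No | Yes | **CRPS** | not CRPS |
| Yes | No | not CRPS | not CRPS |
| Yes | Yes | not CRPS | **CRPS** |

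Pain judged proportionate is never an event under either version. Among patients whose pain is judged disproportionate, the two versions always disagree.

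**3. Effect of false positives at the first visit.** Inputs:

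- *f*, the share of participants falsely positive at that visit, equal in both arms: assumed at 2%, 5% and 10%.
- True risk ratio: assumed at 0.50.
- True control risk p0: assumed at 5%, 10% and 30%. Section 2.2 cites 30% after tibial shaft fracture and up to 37% after distal radius fracture, but gives nothing for the trial's own population.

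Formulas:

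- Observed risk in an arm = f + (1 - f)p.
- False share of all events = f[(1 - p0) + (1 - p1)] / (sum of the two observed risks).

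Example with p0 = 10%, p1 = 5%, f = 5%:

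- Control: 0.05 + 0.95 x 0.10 = 0.145.
- Vitamin C: 0.05 + 0.95 x 0.05 = 0.0975.
- Ratio: 0.0975 / 0.145 = 0.672.
- False share: 0.05 x (0.90 + 0.95) / 0.2425 = 38%.

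| True risks | f | Observed control | Observed vitamin C | Ratio | False share |
|---|---|---|---|---|---|
| 5% v 2.5% | 2% | 6.9% | 4.45% | 0.645 | 34% |
| | 5% | 9.75% | 7.38% | 0.756 | 56% |
| | 10% | 14.5% | 12.25% | 0.845 | 72% |
| 10% v 5% | 2% | 11.8% | 6.9% | 0.585 | 20% |
| | 5% | 14.5% | 9.75% | 0.672 | 38% |
| | 10% | 19.0% | 14.5% | 0.763 | 55% |
| 30% v 15% | 2% | 31.4% | 16.7% | 0.532 | 6% |
| | 5% | 33.5% | 19.25% | 0.575 | 15% |
| | 10% | 37.0% | 23.5% | 0.635 | 26% |

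At 10% v 5%, overall incidence goes from 7.5 per 100 to 12.1 (f = 5%) or 16.8 (f = 10%).

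These are risk ratios. Converting the same risks with ln(1 - p1)/ln(1 - p0) gives hazard ratios of 0.487 with no false positives, 0.655 at f = 5% and 0.743 at f = 10%, so the message is the same on the Cox scale.

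**4. What it would do to a later trial.** This step assumes two-sided alpha 0.05, 80% power, 1:1 allocation and the usual two-proportion formula. True risks of 10% v 5% need 435 per arm; the observed risks need 741 (f = 5%) or 1,080 (f = 10%). At 30% v 15% the figures are 121, 149 and 181.

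**5. Can a later SAP recover the position?** Not with follow-up ended. To test persistence one must know whether a first-visit positive was still positive later, and under section 7.4 that observation is not made.

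**The case against.** **A normal post-operative foot is not counted.** This stands. A reader might infer that swelling and stiffness alone would be locked in as CRPS. They would not: both the text and the form require pain judged disproportionate. The exposure is a misjudgement on that item.

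**Restoring *continuing* would change little.** This largely stands. The protocol gives the word no duration, and pain present since surgery is already continuing at day 10. Section 7.4 also says patients are examined against the full text criteria. The omission is a mismatch to correct, not the main source of error.

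**The form may not be followed literally.** A reader might infer that recorded outcomes will be inverted. The documents do not show that. The form ends with its own yes/no on whether the criteria are met, and section 7.4 diagnoses those who meet the criteria in the text. What the documents show is two rules that conflict.

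**Assessors are trained.** Section 7.4 describes an education session repeated at each rotation and says study researchers conduct follow-up assessments. This lowers the likely error but does not make a wrong call reversible.

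**Requiring a second positive would do harm.** This stands. The synopsis defines the outcome as CRPS at any stage within six months. Positives are referred to physiotherapy, and section 2.2 associates early diagnosis and treatment with better outcomes. A confirmation rule would drop true early cases that improved. A Cox analysis from week 6 would also be unsound while first-visit positives leave follow-up.

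**The stakes are limited.** CRPS is a secondary outcome of an unpowered feasibility study, and the visits follow an earlier wrist-fracture trial and routine care. This sets the weight of the point but does not remove it.

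**Conclusion.** The point holds in a bounded form. One positive at any visit is final, the first opportunity is the early wound check, and removal from follow-up means an early misjudgement cannot be distinguished from CRPS that persists. Separately, the form contradicts the protocol's criteria on the better-explanation item and omits *continuing*.

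With assumed false-positive rates of 5% and 10%, a true ratio of 0.50 would be seen as 0.67 and 0.76 at 10% control risk, or as 0.575 and 0.635 at 30%. The effect is larger at low control risk and modest at high. These figures rest on assumed error rates, equal error in both arms and an assumed true ratio. None of the three comes from the documents, so they show direction and scale and do not predict bias.

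The documents do not support making a second positive a condition of the main outcome. Because CRPS is secondary here, the trial's feasibility aims are not threatened. What is at risk is the incidence and effect estimate carried into a later trial. The change should be made before recruitment, because the missing assessments cannot be recovered afterwards.

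**What to change.** 1. **Section 7.4:** delete the removal from trial follow-up after a positive. Complete the same form at all remaining scheduled visits. This concerns assessment only; referral and treatment are not at issue. It also fits the protocol's adverse-event section, which captures events until 30 days after the final dose (50 + 30 = day 80 of treatment), well past the first two visits.
2. **Section 11.3:** keep CRPS at any visit as the main outcome. Add a sensitivity Cox analysis that does not count positives seen only at the first visit, using the continued assessments. State in advance the event date for those positive again later, and how those with no later assessment are censored. State the caveat that referral after diagnosis may resolve true early cases, so this analysis is not a purer version of the main one.
3. **Form in sections 7.4 and 9.2.2:** align items C and D and the scoring sentence with the criteria in sections 2.2, 3.2 and 7.4.
4. **Visit windows:** reconcile the first-visit window in the synopsis (7-14 days) with that in section 3.2 (10-14 days).

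The cost is a few more form completions at visits the protocol describes as routine, one extra analysis and corrected form wording.
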